Larger, higher quality trials are commonly recommended by authors writing on this matter, and stimulant medication is suggested as deserving of serious consideration as a treatment alternative, despite the limited supporting evidence gathered to date (Orr & Taylor, 2007; Parker & Brotchie, 2009). The literature evaluating research on the use of stimulant medications as monotherapy or for adjunctive use have consistently cited the need for larger, randomized-controlled studies of this treatment modality (Candy, 2009; Dunlop & Nemeroff, 2007; Davidson & Meltzer-Brody, 1999; Carvahlo, 2008).

Questions about both the difficulties encountered with patient medication compliance and abuse of stimulants have been raised (Orr & Taylor, 2007). Misuse of stimulant medication is a commonly held concern by prescribing clinicians. Psychostimulant medications "possess significant abuse potential because of their ability to stimulate brain reward system pathways such as [the] mesocorticolimbic dopamine [pathway]..." (Tremblay, 2002). Lessenger and Feinberg (2007) found that, in 2005, prescribed and OTC medications were intentionally misused or used for non-medical purposes by 6.4 million persons 12 years and older during the past month. Of the medication classes examined for abuse, 1.1 million had misused stimulant medications. Among adults 18-25, the monthly misuse of prescription drugs increased from 5.4% to 6.3%. The authors describe stimulant medications as being of "particular concern:" in 2004, there were 7873 American visits to the ER due to non-medical use of stimulant medications.

Masand, et al, (1998) found no evidence in their case series of drug-seeking, tolerance or dependency among their patients augmented with stimulant medication. Further, our group has over 25 years of experience in the use of stimulant medications for affective disorders; we have not seen any evidence for an increased risk of abuse potential.

Chronically depressed individuals may, additionally, show a compensatory up-regulation of D2 receptors. This up-regulation complicates initial administration of stimulant medication as it may account for the "high" some patients experience with stimulants (Dunlop & Nemeroff, 2007). As depressive physiopathology eases through the initial course of treatment, this up-regulation normalizes.

Mechanism of Action

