- 11) Pregnant or breastfeeding women.

Study Procedures: Figure 3 shows study procedures to be performed at each visit. No study procedures will be performed until a subject signs the informed consent document.

Screen visit (Visit 1): Medical and psychiatric history will be taken, a physical examination and vital signs will be performed and lab tests done. Lab tests include CBC, CMP, urine drug screen and urine pregnancy test for females of childbearing potential. If a subject has had the required lab tests performed within the past 3 months and can produce the results, lab procedures may be waived at the screening visit for that patient (except urine pregnancy test). The HDRS-17 score upon screening will be used to determine entry eligibility (see inclusion criteria). Beyond the patient's verbal report, we will attempt to obtain medical records (e.g., previous clinician or pharmacy records) to document adequate dose and duration of previous/current ADT.

Study Phase 1

Baseline visit (Visit 2): Screened and eligible subjects will return one week after the screening visit. At this visit (provided entry criteria continue to be met) subjects will be randomized in double-blind fashion to one of two treatment groups:

- Group 1: MSA during both phases; or
- Group 2: PBO during Phase 1 followed by MSA during phase 2

Study drug will be dispensed to the subject in sufficient quantity to last until the next study visit (7 days +/-3).

Study visits 3-5: Following the baseline visit, subjects will return at one-week intervals for study visits 3-5. Study procedures to be performed are reflected in Figure 3. Phase 2 study drug is dispensed at study visit 5.

Study visits 6-8: Subjects will return at one-week intervals for study visits 6-8. Study procedures to be performed are reflected in Figure 3. At visit 8, all subjects will receive instructions for tapering the dose of the MSA to avoid potential difficulties from abrupt discontinuation of the study drug.

Study visit 9: Subjects will return two weeks following visit 8 for a safety follow-up check. Procedures to be performed are reflected in Figure 3.

If a subject withdraws or is terminated early from the study, visit 9 procedures will be performed at the final study visit.

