All concomitant medications taken during the study will be recorded in the case report form, along with dosage information and start and stop dates. Subjects requiring excluded drugs will be discontinued from the study. Medication management and clinical ratings will be performed by the study clinicians.

Subjects who complete the trial will be offered referrals to qualified physicians for the purposes of continued care. At the conclusion of Visit 8, study blind will be removed by an unblinded study staff member for facilitation of ongoing treatment by patient's selected follow-up care provider. At Visit 8, study subjects will be provided a one-month prescription for the dose of MSA they are currently prescribed in the study to ease transition to their follow-up care physician.

At the end of the study, subjects will be followed for up to three months while an appointment can be secured with their original treatment provider or with one referred by the research center.

Investigational Product(s), Dose and Mode of Administration, Duration of Treatment with Investigational Product(s): Based upon clinical judgment and ascertained between clinician and patient, study drug will be dosed as follows: The total daily dosage of study drug will be 5-60 mg, supplied in 5 and 10 mg tablets of MSA or matching PBO.

Total daily dosing of the concurrent ADT will be as follows: escitalopram 10-40 mg; fluoxetine 20-80 mg; paroxetine CR 25-100 mg (paroxetine 20-80 mg may be substituted if paroxetine CR is not available); sertraline 100-400 mg; venlafaxine XR 150-600 mg; desvenlafaxine 50-200mg; citalopram 20-80 mg; or duloxetine 60-180 mg; bupropion 150-450 mg; mirtazapine 15-45 mg, tricyclics (standard dosing, individually per label instructions).

The dose of MSA begins at 5mg BID. MSA dose range will be 5mg-20mg BID or TID, not to exceed 60mg per day in addition to the stable dose of ongoing ADT. Each study medication tablet will be 5 or 10 mg of MSA or PBO. Upward titration will be based upon physician's clinical judgment and confirmed by patient's consent.

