Subjects unable to tolerate the study medications will be withdrawn from the study. Every effort will be made to encourage patients to comply with this dosage regimen and to take all study medications and their ongoing concomitant ADT as instructed. All patients will be instructed to return any excess medication at each visit. A pill count will be done to corroborate the study drug record. Protocol violation will be defined as less than 80% compliance by pill count.

MSA doses will be custom-tapered per physician's discretion starting at visit 8.

The study medication packager will use a block randomization scheme to distribute the kits within each box/block.

Risk/Safety Information: The principal investigator and subinvestigators are responsible for monitoring the safety of the subjects who have entered this study and for alerting the IRB of any event that meets IRB reporting criteria. The investigator is also responsible to follow, through an appropriate health care option, adverse events that are serious or that caused the subject to discontinue before completing the study. The subject should be followed until the event resolves or is explained. Frequency of follow-up is left to the discretion of the investigator.

Monitoring and Reporting of Adverse Events and Serious Adverse Events:

Adverse Events:

All observed or volunteered adverse events, regardless of suspected causal relationship to study drug, will be recorded on the case report form and reported to the IRB if reporting criteria are met.

Serious and/or Unexpected Adverse Events:

Study site personnel will report to the IRB any serious and/or unexpected adverse event following IRB reporting guidelines. A serious adverse event is any adverse experience that results in one of the following outcomes, or is significant for any other reason:

- Death
- Initial or prolonged inpatient hospitalization
- A life-threatening experience (that is, immediate risk of dying)
- Severe or permanent disability
- Cancer
- Congenital anomaly

Serious adverse events occurring after a subject is discontinued from the study will not be reported unless the investigator feels that the event may have been caused by the study drug or a protocol procedure.

Unblinding Procedure

Unblinding may be performed only by unblinded site personnel, under two conditions:

- If necessary for treatment of the subject in the event of a medical emergency

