- Upon a subject's completion of the study (visit 8), in order to facilitate continuation of care by a non-study clinician

Monitoring of Study/Oversight:

Study staff will monitor source data and case report forms by regular internal monitoring. .

IRB Review/Ethical Conduct of Study:

IRB Review: Prior to enrolling any subjects, documentation will be obtained that the study protocol and informed consent form have been approved by the Rush University Medical Center Institutional Review Board. Any change in the protocol or informed consent form will require prior written approval except to prevent injury or risk to a subject.

Regulatory Considerations: This study will be conducted in accordance with the ethical principles stated in the most recent version of the Declaration of Helsinki or the applicable guidelines on good clinical practice, whichever represents the greater protection of the individual.

Informed Consent: The informed consent document, in conjunction with verbal discussion of the protocol, will be used to explain the study, including the risks and benefits, to the subject in simple terms before the subject is entered into the study. The investigator is responsible to see that informed consent is obtained from each subject and to obtain the appropriate signatures and dates on the informed consent document prior to the performance of any protocol procedures and prior to any changes made to a subject's medical treatment plan for the purpose of study participation. The original signed consent form will be retained by the investigator.

Confidentiality:

All information collected about subjects for the purposes of this study will be treated as confidential to the extent allowed by law. The information obtained while subjects are enrolled in this study, including all study-related hospital and office records, will be made available to the study doctor, Bristol-Myers Squibb, the Institutional Review Board and other regulatory agencies, including the United States Food and Drug Administration (U.S. FDA).

Intended Use of Data:

The results of this research project may be presented at meetings or in publications, but the identity of subjects will not be disclosed in such presentations.

Statistical Analysis:

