Study Assessments and Primary Endpoints: The difference in absolute change in score from baseline to endpoint in the MGH-CPFQ between the MSA and the PBO groups is the primary endpoint. Key secondary endpoints will be difference in absolute change from baseline in MADRS score between MSA and PBO, difference in remission rates (MADRS < 11) between MSA and PBO, the change from baseline in total score at endpoint of MGH-CPFQ item analysis, difference in change scores on the CGI-S, CGI-I and QIDS. Safety outcome measures: adverse events, physical examinations, vital signs; blood pressure, orthostatic; EKG; Rush Sexual Inventory (RSI).

Statistical Methods: The randomized sample includes all patients who are randomized. The Safety sample will include those randomized patients who received at least one dose of doubleblind study medication as indicated on the dosing record. The efficacy sample will include those patients in the safety sample who have at least one efficacy evaluation post-randomization. The last observation carried forward (LOCF) data set includes data recorded at a given visit after randomization, or, if no observation is recorded at that visit, data carried forward from the previous postrandomization visit. The LOCF data set is primary, and analysis of the observed case data set also will be conducted.

The primary analysis will compare pooled MGH-CPFQ response rates between PBO and MSA and PBO non-responders. Differences in response rates will be compared using the CMH General Association Test. Descriptive statistics on non-primary groups will be conducted.

This study seeks to estimate the strength of any statistically significant relationship, or effect size, in addition to statistical significance of found treatment effects.

Secondary Endpoints Analysis: Differences in remission (defined as an endpoint MADRS score <11) rates will be compared using the CMH General Association Test. Logistic regression analysis will be performed to explore the relationship between response and patients' demographics and prognostic variables including baseline QIDS score, gender, site, and age, etc. Similar analyses will be performed for remission.

Fig. 3	: Stud	y Proce	dures	Table
--------	--------	---------	-------	-------

			Treatment period 1			Treatment period 2			
Study Visit	V1 Screen	V2 Baseline	V3	V4	V5	V6	V7	V8	V9 F/UP
End of Week	-1	0	1	2	3	4	5	6	8
Day	-7	0	7	14	21	28	35	42	56
Informed consent	Х								
Demographic data	Х								

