Medical and psychiatric history	Х	Х							
SCID	х								
Physical exam	Х								
Vital signs and weight	Х	Х	Х	Х	Х	Х	Х	Х	Х
EKG	Х								Х
Lab tests*, urine pregnancy test** and urine drug screen	х								х
MGH-ATRQ	Х								
Inclusion/exclusion criteria	Х	Х							
Randomization		Х							
Expectation ratings		Х							
Clinician-completed surveys:									
HDRS (17- and 28-item)	Х	Х						Х	
MADRS		Х	Х	Х	Х	Х	Х	Х	
CGI-S	х	Х							
CGI-I			Х	Х	Х	Х	Х	Х	
C-SSRS	х	Х	Х	Х	Х	х	Х	Х	х
Patient-completed surveys:									
MGH-CPFQ	Х	Х	Х	Х	Х	Х	Х	Х	
EWPS	х	Х	Х	Х	Х	х	Х	Х	
Fawcett EPI	Х	Х	Х	Х	Х	Х	Х	Х	
FASD	Х	Х	Х	Х	Х	Х	Х	Х	
HSQ 2.0	Х	Х	Х	Х	Х	Х	Х	Х	
PGI-S	х	Х							
PGI-I			Х	Х	Х	Х	Х	Х	
RSI	Х	Х	Х	Х	Х	Х	Х	Х	
QIDS-16	Х	Х	Х	Х	Х	Х	Х	Х	
SANS	Х	Х	Х	Х	Х	Х	Х	Х	
SDS	Х	Х	Х	Х	Х	Х	Х	Х	
SF-36	Х	Х	Х	Х	Х	Х	Х	Х	
Study drug dispensed		Х	Х	Х	Х	Х	Х	Х	
Study drug accountability			Х	Х	Х	Х	Х	Х	Х
Concomitant therapy	Х	Х	Х	Х	Х	Х	Х	Х	Х
Adverse events	Х	Х	Х	Х	Х	Х	Х	Х	Х

*Including CBC and CMP. If patient can produce lab results for CBC and CMP performed within the past 3 months, screening procedures may be waived. **For females of childbearing potential

- Angst J. (1992). How recurrent and predictable is depressive disorder? In: Montgomery S, Rouillon F, eds. *Long-term treatment of depression perspectives in psychiatry*. Chichester, UK: John Wiley & Sons Ltd., Vol. 3, p.13.
- Carvalho AF, Machado JR & Cavalcante JL (2008). Augmentation strategies for treatmentresistant depression. *Current Opinion in Psychiatry*, 22 : 7–12.
- Chiarello RJ & Cole JO (1987). The use of psychostimulants in general psychiatry. *Archives of General Psychiatry*, 44, 286-295.

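### No EKG is scheduled during treatment, and completers' only post-baseline EKG (V9) falls at an undetermined MSA exposure and gives no placebo contrast

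*Combined protocol and SAP*

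**What the plan says.** Research Hypotheses, item 2a, names significant EKG change among the measures on which MSA is to show acceptable safety against placebo. The Statistical Analysis section lists it again: "Safety outcome measures: adverse events, physical examinations, vital signs; blood pressure, orthostatic; EKG; Rush Sexual Inventory (RSI").

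The EKG row of Fig. 3 is marked at V1 and V9 and nowhere else. V9 comes two weeks after Visit 8. A subject who leaves early has the V9 procedures at the final visit instead.

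Three statements govern MSA after Visit 8:

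- Study Procedures, Study visits 6-8: "At visit 8, all subjects will receive instructions for tapering the dose of the MSA", so that the drug is not stopped abruptly.
- Study Procedures, on subjects who complete the trial: at Visit 8 "study subjects will be provided a one-month prescription for the dose of MSA they are currently prescribed in the study", to ease the handover to follow-up care.
- Investigational Product(s), Dose and Mode of Administration: "MSA doses will be custom-tapered per physician's discretion starting at visit 8".

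Group 1 takes MSA in both phases. Group 2 takes placebo in Phase 1 and MSA in Phase 2.

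**The concern.** An EKG outcome meant to compare MSA with placebo needs readings taken while one arm is on MSA and the other on placebo. The schedule has none. The one post-baseline reading in completers comes after the treatment period, when both arms have had MSA and when the text does not settle whether a subject is still taking it. The taper statements point to a falling or zero dose, whereas the prescription points to the full Visit 8 dose.

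At stake is how the EKG result can be read. An unchanged V9 EKG would not show that MSA leaves the EKG unchanged during treatment, because the subject may be off drug. A changed V9 EKG could not be attributed by comparison with placebo, because completers have no placebo group by then.

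**Working it through.** The plan gives no figure to reproduce. The check is a reading of the schedule with short arithmetic.

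**1. EKG coverage (Fig. 3).** EKG is marked at 2 of 9 visits (V1, V9). At the on-treatment visits V3 to V8 the count is 0 of 6. Vital signs with weight, and adverse events, are marked at 6 of 6.

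**2. Timing of V9 against the prescription.** V8 is day 42 and V9 is day 56, so the gap is 56 - 42 = 14 days. If the ±3-day window stated for weekly visits also applies to V9 (an assumption), the gap is 11 to 17 days. Taking one month as 28 to 31 days (an assumption), the supply left at V9 runs from 28 - 17 = 11 days to 31 - 11 = 20 days. A subject who follows the prescription is therefore at full dose at V9.

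**3. Possible exposure at V9.** Under the prescription, it is the Visit 8 dose, anywhere in the protocol's 5-60 mg/day range. Under the taper statements, it is a reduced dose or none, since no taper length is given. No text assigns subjects to one course or the other. The supply is also unclear: Fig. 3 marks study drug dispensed at V8, but Fig. 1 shows dispensing at V2 to V7 and not at V8.

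**4. What an EKG would show at each candidate visit, in subjects still in the study.**

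| Visit | Group 1 | Group 2 | What it supports |
|---|---|---|---|
| V5 (day 21, end of Phase 1) | MSA | placebo | randomised MSA-versus-placebo contrast |
| V8 (day 42, before taper) | MSA | MSA | on-drug reading, no placebo contrast |
| V9 (day 56) | undetermined | undetermined | neither |

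**5. Precision, for scale only.** If no abnormal EKG is seen among m subjects known to be on MSA, the exact one-sided 95% upper bound on the abnormality rate is 1 - 0.05^(1/m).

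- V8, all 40 randomised subjects complete: m = 40, bound 7.2%.
- V8, 24 completers (assumed equal to the stated minimum of evaluable subjects): m = 24, bound 11.7%.
- V5, MSA arm only: m = 20, bound 13.9%; m = 12, bound 22.1%.

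At V9, m is the number still taking MSA. The documents neither give nor determine it, so no bound can be stated in advance.

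**The case against.** **The Visit 8 statements can be read together.** A physician with discretion over the taper can use a month's supply either to continue or to step down. Subjects are also followed for up to three months while an appointment is secured. This largely stands: an individualised taper is a legitimate choice, and what is missing is a sentence linking the statements. A reader might infer that the missing taper rule is what makes the EKG evidence weak. The documents do not support that. With a perfect taper rule there would still be no EKG at V3 to V8, and V9 would still offer completers no placebo contrast.

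**Exposure at V9 is recorded.** Fig. 3 marks concomitant therapy and drug accountability at V9, and the protocol states: "All concomitant medications taken during the study will be recorded in the case report form". A reader might infer that MSA filled by prescription escapes this, because the Unblinding Procedure speaks of "completion of the study (visit 8"). That is strained. Participation is defined as nine visits over nine weeks, so V9 lies within the study. Recording exposure describes the mixture, however, and does not remove it.

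**Misuse.** The background says "Misuse of stimulant medication is a commonly held concern by prescribing clinicians", and a reader might infer that the prescription creates a misuse hazard, or that the V9 urine drug screen will be uninterpretable. The same background goes on to report no drug-seeking or dependency in a case series and no sign of increased abuse risk in the group's own experience. Current substance use disorder and positive drug screens are exclusions. The screen's panel is not stated, and no text uses it to judge tapering. Neither inference is part of this point.

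**The sample is small wherever the EKG is placed.** This stands. Even the best case above leaves a bound of 7.2%. Moving the EKG makes the reading interpretable but not precise.

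**A follow-up EKG has value for the individual subject.** This also stands, and it is the cost of moving the EKG.

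**Conclusion.** The point holds and is minor. As scheduled, completers have 0 EKGs at six on-treatment visits. Their single post-baseline EKG is taken at an exposure that can range from none to the full Visit 8 dose. That reading cannot answer the EKG part of hypothesis 2a, whatever the taper rule.

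The finding rests on the marks in Fig. 3, the Phase 2 assignment and the three Visit 8 statements. The days of supply left and the precision bounds rest on the assumptions labelled in the working, and the finding does not depend on them.

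No efficacy endpoint is touched. Vital signs, weight and adverse events are collected throughout treatment and do not rely on V9. Early terminators may supply some on-treatment EKGs at their final visit, but they are a self-selected group and give no randomised comparison.

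**What to change.** **Move the planned completer EKG from V9 to an on-treatment visit.** There are two options:

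- V5, before the first Phase 2 dose. This gives the randomised contrast that hypothesis 2a asks for, and is preferable if that hypothesis is kept. It leaves Group 2 completers without an EKG on MSA.
- Visit 8, before any taper. This gives an on-drug reading in both groups and no placebo contrast.

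Early terminators keep the EKG at their final visit. Moving it adds no procedure and costs the follow-up reading. Keeping V9 and adding one of the two costs one EKG per completer: 24 to 40 in all, if completers number between the stated evaluable minimum and the number randomised.

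**Reconcile the Visit 8 text.** State that the prescription bridges subjects whom the physician judges should continue, and that all subjects keep taper instructions for when they stop. Withholding those instructions from continuing subjects would remove a safeguard should follow-up care not be in place when the supply ends. Make Fig. 1 and Fig. 3 agree on dispensing at V8.

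**Record MSA dose and last-dose date at V9**, with the concomitant therapy already collected there. This and the reconciliation are wording changes plus one explicit case report form entry.

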- **Study Design:** A randomized, double-blind, placebo-controlled, parallel-group study of flexible dose mixed salts amphetamine (5-60 mg) adjunctive to antidepressant therapy among adult outpatients with major depressive disorder responding inadequately to current antidepressant therapy.

Fig. 1: Treatment Groups

Visit	Phase	Weeks	Group	Group	Procedures
		on med	1	2	
V1		Scr			Inclusion/Exclusion
V2		0			Baseline measurement + disp.
V3	Ι	1	MSA	PBO	Measure effect of 1 week on study med + disp.
V4	Ι	2	MSA	PBO	Measure effect of 2 weeks on study med + disp.
V5	Ι	3	MSA	PBO	Measure effect of 3 weeks on study med + disp.
V6	II	4	MSA	MSA	Measure effect of 3 weeks on study med + disp.
V7	II	5	MSA	MSA	Measure effect of 3 weeks on study med + disp.
V8	II	6	MSA	MSA	Measure effect of 3 weeks on study med
V9		(8)			Safety follow-up

Fig. 2: Study Design Overview

The treatment phase of the study consists of 2 phases (21 treatment days per phase). Study Phase 1 will consist of visits 2 (baseline) through 5. Study Phase 2 will consist of visits 6 through 8. There will be a follow-up visit 2 weeks following visit 8. There is a one-week interval between study visits, with a scheduling window of \pm 3 days allowed.

Mixed salts amphetamine is FDA-approved for Attention Deficit-Hyperactivity Disorder (ADHD) and superior in efficacy to placebo; therefore, comorbid ADHD will be statistically controlled as a continuously-variable covariate, but will not be considered an exclusionary condition.

The primary analysis will be a repeated measures analysis of variance using a mixed-effects model (PROC MIXED-MMRM). The primary outcome measure will be the MGH-CPFQ total score at baseline and the MGH-CPFQ total score at the end of the trial. The independent variables will be the study visit, the treatment in the previous phase, and treatment assignment. The variance covariance matrix for the repeated measures will be unspecified.

Enrollment Period: The enrollment period is estimated to be 6 months. The last patient is expected to complete the study by March 31, 2010.

Number of Subjects: 40 subjects will be randomized (20 to each treatment arm). Additional subjects may be consented to allow for screen failures. Subjects who terminate early post-randomization will be replaced only sufficiently to ensure a total number of 24 (12 to each treatment arm) evaluable subjects.

Duration of Subjects' Study Participation: There will be a total of 9 study visits over a period of 9 weeks.

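### An early exit calls only for the visit 9 safety procedures, with no efficacy scale, and LOCF has no limit where Group 2 changes from placebo to MSA

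*Combined protocol and SAP*

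**What the plan says.** **Exit rule.** Under Study Procedures, after Study visit 9: "If a subject withdraws or is terminated early from the study, visit 9 procedures will be performed at the final study visit". The protocol describes visit 9 as a safety check and refers to Fig. 3 for its content. The V9 column of Fig. 3 marks vital signs and weight, EKG, laboratory and urine tests, C-SSRS, drug accountability, concomitant therapy and adverse events. In the block headed "Clinician-completed surveys", MADRS and CGI-I run to V8 and only C-SSRS is marked at V9. In the block headed "Patient-completed surveys", MGH-CPFQ and QIDS-16 run to V8 and nothing is marked at V9.

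**Missing data.** Statistical Methods fills gaps as follows: "if no observation is recorded at that visit, data carried forward from the previous postrandomization visit". It then states: "The LOCF data set is primary, and analysis of the observed case data set also will be conducted". Membership of the efficacy sample is also defined there: "The efficacy sample will include those patients in the safety sample who have at least one efficacy evaluation post-randomization".

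**Treatment sequence.** Group 2 takes placebo in Phase 1 and MSA in Phase 2. Phase 2 drug is handed out at V5, and Fig. 1 labels V6-V8 as MSA for both groups.

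**Endpoint and primary analysis.** Study Design says: "The primary outcome measure will be the MGH-CPFQ total score at baseline and the MGH-CPFQ total score at the end of the trial". It names a mixed model for repeated measures (MMRM) as primary. Study Assessments and Primary Endpoints defines the endpoint as the difference in "absolute change in score from baseline to endpoint in the MGH-CPFQ between the MSA and the PBO groups" and names no visit. Statistical Methods describes the primary analysis as a CMH comparison of pooled response rates.

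**The concern.** Two written rules, if followed, lose or mislabel efficacy data.

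First, the only instruction for an early leaver points to a visit without efficacy scales. Subjects who cannot tolerate study drug are withdrawn, and that can happen between weekly visits. The primary scale is then not required at the moment of leaving, and no later analysis can recover a score that was never taken.

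Second, V5 is the last placebo rating in Group 2 and V6 the first on MSA, but the carry-forward rule ignores that boundary. A placebo score can therefore stand in for an MSA score in the data set that the plan calls primary.

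The two gaps also meet. A Group 2 subject who stops between V5 and V6 with no exit rating is represented at V6 by a placebo score.

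**Working it through.** The plan states no dropout rate, effect size or SD, so there is no figure of its own to reproduce. The first two steps are readings of the text, and the rest is arithmetic under stated assumptions.

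1. **What an exit visit must contain.** The V9 column marks seven rows. C-SSRS is the only rating scale among them, and it is not listed as an efficacy outcome in the hypotheses or the endpoint section. Nothing suspends the scales due at a scheduled V3-V8 visit. The gap is therefore limited to unscheduled exits and to sites that do the V9 list in place of the scheduled one. Visits are 7 days apart with a window of 3 days either way, so:
   - the first post-randomization scale falls at day 7 (7 - 3 = 4 to 7 + 3 = 10);
   - at an exit between visits, the last MGH-CPFQ is up to 7 days old nominally and up to 10 at the limit of the window;
   - each leaver before V3 without a rating removes 1/20 = 5% of an arm from the efficacy sample.

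2. **How far LOCF can carry a placebo score.** If the previous visit means one visit back only, a V5 score still fills V6. Under ordinary LOCF, a V3-V5 score fills V6, V7 and V8.

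3. **Range for the illustration.** Number of Subjects gives 20 randomized per arm, with replacement only to keep 12 evaluable per arm. 20 - 12 = 8, and 8/20 = 40% per arm could go unreplaced, if evaluable means completer (the term is not defined). This is a tolerance, not a forecast.

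4. **V8 contrast, Group 1 minus Group 2, ordinary LOCF.** Assume that MSA has the same effect d in both arms, that d is fully reached by V8, that placebo scores contain none of it, and that Group 1 is complete. Let f be the fraction of Group 2 whose last rating is at or before V5.
   - Group 1 mean effect = d
   - Group 2 mean effect = d(1 - f)
   - Shift = d - d(1 - f) = +f·d, where the true difference is 0

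| Group 2 leavers of 20 (assumed) | f | Shift |
|---|---|---|
| 2 | 0.10 | +0.10d |
| 4 | 0.20 | +0.20d |
| 6 | 0.30 | +0.30d |
| 8 | 0.40 | +0.40d |

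5. **Pooled MSA against placebo.** If Phase 2 scores are instead pooled as MSA results, Group 2 contributes d(1 - f) where it should contribute d. The carried placebo scores then dilute the MSA effect. The plan does not describe the pooling well enough to put a total on this.

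6. **Cases with no effect on the primary result.** With a V5 endpoint, no value crosses the boundary before the endpoint, so the carry-over shift is 0. With MMRM on unimputed data it is also 0, because that model needs no carry-forward. If MMRM were run on the LOCF data set with Phase 2 visits included, the carried scores would enter.

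**The case against.** The strongest reply is that neither gap need touch the primary result. Study Design names MMRM, which needs no LOCF. The endpoint may be V5, the last visit at which the arms differ in treatment. An observed-case analysis is also planned. This largely stands for the second gap: the effect on the primary result is conditional on conflicts that the plan has not resolved. It does not remove the point, because Statistical Methods calls the LOCF data set primary, and LOCF summaries of V6-V8 mix placebo with MSA scores whatever the endpoint. Observed-case analysis is a partial check and cannot restore an exit score that was not taken. A missing exit rating in Phase 1 matters for a V5 endpoint too.

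It is also fair to say that the V9 procedures are most naturally read as added to the scheduled ones. That narrows the first gap but leaves unscheduled exits uncovered.

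A reader might infer that the direction of the carry-over shift depends on which arm loses more subjects. It does not. If a fraction g of Group 1 also leaves in Phase 1 having reached a fraction r of the effect, the V8 shift is d(f - g(1 - r)). The placebo carry-over is the f term alone, and in this contrast it is never negative. The g term is ordinary early-exit LOCF from MSA to MSA. Nor does the larger loss set the sign of the total: f = 0.20, g = 0.30, r = 0.5 gives 0.20 - 0.15 = +0.05d, although Group 1 loses more.

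**Conclusion.** Both gaps are in the text and both are cheap to close.

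For the exit visit, the loss is limited to unscheduled exits or a substitution reading, and no bias size is claimed. A reader might infer that early leavers never give an exit rating. The documents do not support that, since scheduled scales remain due.

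For LOCF, a placebo score can be counted at V6 on any reading, and through V8 under ordinary LOCF. The effect on the primary result is zero with a V5 endpoint or MMRM on unimputed data. In a V8 contrast of Group 1 against Group 2 it is +f·d, so +0.10d to +0.40d under the stated assumptions. In a pooled MSA-against-placebo comparison the effect is dilution of MSA.

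A reader might take +0.40d as the expected bias. It is an extreme case: 8 of 20 leave during the placebo phase and none leave Group 1, whereas withdrawal for intolerance would point more towards exits on MSA. The V8 figures also fall away if carry-forward reaches only one visit.

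**What to change.** 1. **Exit ratings.** Require MGH-CPFQ, MADRS, QIDS-16 and CGI-I at early termination, in addition to the V9 safety procedures. Assign these scores by a stated window to a visit of the same phase. The cost is a slightly longer exit visit, at a visit that already takes place.

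2. **LOCF limit.** Add one sentence to the LOCF definition: no Phase 1 value is carried into V6-V8. Phase 1 leavers then count in the Phase 1 LOCF data (V3-V5) only. This costs 3 imputed values (V6, V7, V8) per Phase 1 leaver in either arm. With 8 leavers in each arm that is 2 × 8 × 3 = 48 of 40 × 3 = 120 Phase 2 values. Phase 2 LOCF results would then describe only subjects with a Phase 2 score. They are no longer a full randomized comparison and must be labelled so.

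3. **Reconcile at the same time.** Name the endpoint visit, and settle whether MMRM or the CMH test on the LOCF data set is primary. If V8 were kept as the primary time point, the limit in item 2 would condition the primary contrast on staying beyond Phase 1. Labelling does not solve that selection problem, so the choices need to be made together.
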